# Venous Clinical Severity Scoring (VCSS)

The VCSS is an extension of the CEAP classification and has been designed as an evaluative tool for the assessment of CVD. The VCSS (appendix 4 Datasheet) consists of 10 categories, pain, varicose veins, oedema, skin pigmentation, inflammation, induration, ulceration (number, size and duration) and use of compression therapy, which are scored on a severity scale from 0 to 3.

#### Eykona® Wound Measurement System

Skin changes associated with lipodermatosclerosis such as erythema, induration, hyperpigmentation and white atrophy, will be measured using the Eykona® Wound Measuring System (Type EYK10001). This system (Appendix 4 Datasheet) contains a 3D portable camera with software that enables precise measurements of wound size and tissue condition. Photographs will be taken at each visit. The length and width are measured and the surface area of the different skin changes will be calculated.

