# Background

Chronic venous disease (CVD) has various clinical presentations and the most commonly known symptom is varicose veins. Other symptoms include pain, oedema, and cutaneous changes of the lower legs such as hyperpigmentation, eczema, atrophie blanche (white scar tissue) and lipodermatosclerosis (induration caused by the fibrotic process of the subcutaneous fat). Chronic venous disease can be classified with the clinical, aetiologic, anatomical, and pathophysiological classification (CEAP-classification) in which the clinical signs are graded into six classes; C0-C6 (Table 1). CVD includes all symptoms and signs, whereas chronic venous insufficiency (CVI) refers to a more advanced stage of CVD (i.e. C4-C6) (12).

C0	No visible or palpable signs of venous disease
C1	Telangiectasies or reticular veins
C2	Varicose veins
C3	Oedema without skin changes
C4a`	Pigmentation or eczema
C4b	Lipodermatosclerosis or atrophie blanche
C5	Healed venous ulcer
C6	Active venous ulcer

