# Statistical analysis

Statistical analysis will be performed using SPSS version 20.0 or higher. The CEAP classification, the Venous Clinical Severity Score and the AVVQ score at the 2, 4, and 8 weeks assessment will be compared with the baseline scores. The length, width and surface area of the skin condition from the leg with the copper will be compared with the control leg and the measurements at the 2, 4, and 8 weeks assessment will be compared with the baseline measurements. Paired t-test will be used for continuous data at baseline and a multilevel (mixed) regression model will be used to analyse the change over time.

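### For the skin objective, the only stated copper-versus-control comparison is photographic extent, which cannot show softening or fading inside an unchanged border; the per-leg VCSS skin grades have no leg comparison

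*Combined protocol and SAP*

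**What the plan says.** The secondary objective is the effect of copper stockings on skin condition in lipodermatosclerosis. Each patient wears a copper stocking on one leg and a non-copper compression stocking on the other. These parts of the combined protocol and SAP bear on how the objective is answered:

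- **Background.** The disease is defined as "lipodermatosclerosis (induration caused by the fibrotic process of the subcutaneous fat".
- **Eykona Wound Measurement System.** Four features are named: "Skin changes associated with lipodermatosclerosis such as erythema, induration, hyperpigmentation and white atrophy, will be measured using the Eykona" system. The quantities taken are then given: "The length and width are measured and the surface area of the different skin changes will be calculated". The device is credited with "software that enables precise measurements of wound size and tissue condition", but no colour, depth or firmness variable is defined.
- **Venous Clinical Severity Scoring (VCSS).** The ten categories, each scored 0 to 3, include "skin pigmentation, inflammation, induration". The section on patient data, history and physical examination says the scoring is done for each leg individually, at each visit.
- **Statistical analysis, photographs.** "The length, width and surface area of the skin condition from the leg with the copper will be compared with the control leg", and follow-up measurements are also compared with baseline.
- **Statistical analysis, scores.** For CEAP and for the other scores, "the Venous Clinical Severity Score and the AVVQ score at the 2, 4, and 8 weeks assessment will be compared with the baseline scores". No comparison between legs is stated. A mixed regression model is planned for change over time, with no outcome, leg term or contrast named.

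**The concern.** The disease is defined by hardness of tissue under the skin, and the one measure assigned to the copper-versus-control question describes the outline of visible changes. An improvement in firmness or colour intensity that leaves the outline where it was would not appear in that comparison. The scale that could show it is collected on each leg, but the plan gives it a comparison that does not separate the copper leg from the control leg.

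At stake is whether the pilot can answer its secondary objective. The Sample size calculation section says the data will support a power calculation for a larger multicentre study, so an endpoint that is blind to part of the hypothesised effect could be carried into that study.

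**Working it through.** The sample size of 15 comes from expected recruitment over three months. No alpha, power, effect size or standard deviation stands behind it, so there is no planned figure to reproduce. The check is of what each stated comparison can detect.

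**Step 1. What the photographic measures register.** Let L, W and A be the length, width and surface area of a skin change on one leg. All three are functions of its border. If the border is the same at baseline and follow-up, then ΔL = ΔW = ΔA = 0, however much the tissue inside has softened or faded. If the border also moves, the measures register that part only.

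**Step 2. What a comparison with baseline estimates for VCSS.** Write the mean change from baseline as

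- control leg: c
- copper leg: c + k

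Here c is everything common to both legs (compression, time, observer drift, regression to the mean) and k is the copper effect. Then:

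| Comparison | Estimates |
|---|---|
| Copper leg, follow-up minus baseline | c + k |
| Both legs together, follow-up minus baseline | (c + c + k)/2 = c + k/2 |
| Copper-leg change minus control-leg change | (c + k) − c = k |

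Only the third line isolates k. It is stated for length, width and area, and not for VCSS.

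**Step 3. Coverage of the secondary objective, from the text.**

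| Feature | Extent by photograph | Severity by VCSS, per leg | Stated leg comparison |
|---|---|---|---|
| Induration | listed, but only as length, width, area | yes, 0–3 | extent only |
| Pigmentation | length, width, area | yes, 0–3 | extent only |
| Erythema / inflammation | length, width, area | yes, 0–3 | extent only |

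**Step 4. Illustration of size.** Assumptions, none of them from the documents except n: paired t-test on the leg difference, n = 15 pairs, two-sided alpha 0.05, all patients complete. With noncentrality d√15 and 14 degrees of freedom, 80% power needs a standardised paired difference of d = 0.78. The normal approximation, (1.960 + 0.842)/√15, gives 0.72. Suppose the true effect is 0.78 and only a share s of it moves the border, with the standard deviation unchanged. The photographic comparison then sees 0.78 × s:

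| Share s that moves the border | Power |
|---|---|
| 1 | 80% |
| 0.75 | 56% |
| 0.5 | 29% |
| 0.25 | 11% |
| 0 | 5% |

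The last row is the false-positive rate, and it stays at 5% whatever the sample size. The documents give no information on s.

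**The case against.** The strongest reply is that softening and fading are not lost. VCSS grades them on each leg at every visit, and the plan analyses VCSS at 2, 4 and 8 weeks. That stands, and it rules out the stronger reading that a leg improving inside its border would count as no effect anywhere in the analysis. The change would be recorded and analysed over time; what is missing is its attribution to copper. The mixed model might include a leg term, but none is stated.

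A related reply is that the Background says standard stockings do not improve skin condition, so c might be taken as zero for the skin items. But c also contains time and observer effects, and the control leg exists so that this need not be assumed. For VCSS as a whole the reply fails on the plan's own account, since the Background says compression reduces pain and oedema, both of which are VCSS categories.

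Other stronger readings are tempting, and the documents do not support them:

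- *A single pooled lesion area will be analysed, so that one change turning into another is hidden.* The Statistical analysis section uses the singular, but the Eykona section refers to the different skin changes in the plural. Loose wording is the likelier explanation.
- *The skin items enter only through the VCSS total, and are diluted there.* The plan does not say that only the total is used. Setting a one-grade gain in three items as 3/9 (33%) against 3/30 (10%) only changes the denominator; it is 3 points either way. The three ulcer categories should start at zero, because current ulceration is excluded, and compression is worn on both legs. Those four categories, 12 of 30 points, should add little noise between legs.
- *The camera cannot assess tissue.* The device is credited with measuring tissue condition, and its datasheet appendix is not in the text reviewed. The point concerns the quantities named for analysis.

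Entry requires CEAP 4, which includes C4a (pigmentation or eczema), so some legs may have no induration and that limitation need not apply to every patient. Finally, this is a secondary objective in a pilot, which limits the weight of the point but not its correctness.

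**Conclusion.** The point holds as a gap in the planned analysis. For the skin objective, the only stated between-leg comparison uses measures of extent, which change by exactly zero for improvement inside a fixed border. The VCSS grades that could show such improvement are compared only with baseline, which estimates c + k or c + k/2 and not k.

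The zero follows from the measures themselves. The fall in power from 80% to 5% rests on the assumed test, alpha, effect and unchanged standard deviation, and is an illustration only. How often improvement would occur without a border change is unknown from the documents, so no overall loss can be stated. A reader might infer that the trial cannot detect a skin effect at all. It can detect one that moves the border, and it already collects the data for the rest. The change is worth making because it costs little and lets the pilot answer its secondary objective.

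**What to change.** 1. **Statistical analysis.** Prespecify a copper-versus-control comparison of change from baseline in the per-leg VCSS pigmentation, inflammation and induration items: their sum (3 items × 0–3, range 0–9), with induration also shown alone. Report it alongside photographic area. Use the same mixed model for both, with terms for leg treatment (copper or control) and visit, and with legs paired within patient.
2. **Eykona section.** State that induration is graded by clinical examination within the VCSS, and that photographic area measures only the extent of visible changes.
3. **Statistical analysis, wording.** Replace the singular skin condition with the plural skin changes of the Eykona section, so that the two agree.

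Cost: analysis wording only. The items are already scheduled on each leg at every visit, by clinicians blinded to the copper stocking. The grades are coarse and ordinal, and this is one more secondary analysis in 15 patients, so the results should be labelled exploratory. The three-item sum is not described in the protocol, so it should sit beside photographic area and not replace it.

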# Methodology

This is a randomised controlled pilot study to assess the feasibility of copper impregnated stockings. All patients with CEAP classification 4 in both legs and venous disease identified by venous duplex will be recruited from the vascular clinics within Croydon Health Services over a period of three months. All patients will be given a patient information sheet describing the study prior to consent (Appendix 1 Patient Information Sheet). Patients will be giving adequate time to read the information. Informed consent and the agreement for photography of their legs will be obtained (Appendix 2 Informed Consent). Patients will be assessed at baseline and at 2, 4 and 8 weeks follow-up.

The inclusion criteria are:

- Male or female patients
- CEAP classification 4 in both legs
- Venous disease identified by venous duplex
- Ability to understand and read the patient information sheet (in English)
- Ability to give informed consent

The exclusion criteria are:

- Inability to give consent
- Pregnancy
- Current ulceration
- Wilson's disease
- Allergy to copper
- Arterial insufficiency of the lower extremities

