# Copper impregnated stockings

All patients will be asked to wear compression stockings (14-18mmHg). These closed-toe and below-the-knee stockings are made of 88% nylon, 5% elastin, and 7% spandex and come in various sizes. One of the pair will have copper oxide ions permanently attached to

CIVIL Protocol Version 3 (25/03/2015) 15/LO/0974

the nylon fibres and these stockings will contain 2-3% copper ions. The patients will wear a copper stocking on one leg (study leg) and a non-copper stocking on the other (control leg). Both the patients and the clinicians will be blinded to the copper impregnated stocking.

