# Patient data, history and physical examination:

Demographic data such as age, ethnicity, height and weight will be collected (Appendix 3 Datasheet). Past medical history such as concomitant (chronic) diseases and the use of medications will be obtained. At each visit, subjective symptoms will be obtained using the Aberdeen Varicose Veins Questionnaire (AVVQ). For obtaining objective signs, the CEAP classification and the Venous Clinical Severity Scoring (VCSS) will be performed for grading the severity of the venous insufficiency per leg individually, and photographs with the Eykona® 3D camera will be taken. All datasets will be coded and anonymised. The data will be stored in a secure room within the Trust. All electronic data will be stored within password protected IT system within the Trust, which is only accessible by the clinical and research team.

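### No masking of visit is described when skin areas are measured from photographs, which leaves the planned comparison with baseline open to expectation or reading drift

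*Combined protocol and SAP*

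**What the plan says.** The Eykona® Wound Measurement System section describes a device that "contains a 3D portable camera with software that enables precise measurements of wound size and tissue condition" and applies it to the skin changes of lipodermatosclerosis. "Photographs will be taken at each visit", and then "The length and width are measured and the surface area of the different skin changes will be calculated". The visits are set in Methodology: "Patients will be assessed at baseline and at 2, 4 and 8 weeks follow-up". The protocol does not say who measures, how many readers there are, whether borders are traced by hand or found by the software, when and in what order images are read, or whether the reader can see which visit an image comes from.

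The only blinding statement is in Copper impregnated stockings: "Both the patients and the clinicians will be blinded to the copper impregnated stocking". The patient data section adds "All datasets will be coded and anonymised". That deals with identity; it does not say that visit or date is hidden from the person measuring.

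Statistical analysis plans two comparisons of the skin measurements. One is between legs: "The length, width and surface area of the skin condition from the leg with the copper will be compared with the control leg". The other is over time: "the measurements at the 2, 4, and 8 weeks assessment will be compared with the baseline measurements". Under Randomisation, the envelope that holds the allocation is guaranteed to stay sealed only while recruitment is open.

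**The concern.** The two planned comparisons need different protection. Not knowing which leg has copper protects the comparison between legs. It does not protect the comparison over time, because a reader who cannot tell copper from control may still know which image is the baseline one.

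There are two reasons to care here. First, Methodology excludes patients with current ulceration, so a system described for wounds is applied to skin changes that have no open wound edge. The protocol gives no repeatability data for that use. If an operator decides where such a change ends, there is room for judgement. Second, the Background says when improvement should appear: within two weeks, and probably never if nothing has changed by four. A reader who knows the visit therefore has something to expect.

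At stake is the change from baseline in skin area, which serves the secondary objective. The pilot data are also meant to support a power calculation for a larger multicentre study, so a false change could be carried forward into that calculation.

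**Working it through.** **The plan's own figure.** The only number to reproduce is the sample size of 15. It comes from expected recruitment over three months, not from a calculation, so no formula can be checked. No alpha, standard deviation or repeatability is given.

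**1. What the stated blinding covers.**

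| Planned comparison | What the reader must not know | Stated in the protocol? |
|---|---|---|
| Copper leg versus control leg | Which leg has copper | Yes |
| Weeks 2, 4 and 8 versus baseline | Which visit the image is from | Not described |

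**2. Amount of reading.** 15 patients × 2 legs × 4 visits = 120 leg assessments.

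**3. Apparent change in area.** Assume that area scales as length × width, that there is no true change, and that each dimension is read a fraction f shorter at follow-up. The apparent reduction is 1 − (1 − f)².
- f = 5%: 1 − 0.95² = 0.0975, about 10%.
- f = 10%: 1 − 0.90² = 0.19, or 19%.

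Both values of f are assumptions. Nothing in the protocol bears on their size or direction.

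**4. Effect on a test against baseline.** As a simple stand-in for the planned mixed model, take a paired t-test of one follow-up visit against baseline, with n = 15, assumed two-sided alpha 0.05 and no true change. Let the reading drift be d, in standard deviations of the change score. The statistic then follows a noncentral t distribution with 14 degrees of freedom and noncentrality d√15.

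| Drift d (SD) | False-positive rate |
|---|---|
| 0 | 5.0% |
| 0.1 | 6.5% |
| 0.25 | 14.7% |
| 0.5 | 43.8% |
| 0.75 | 77.1% |
| 1.0 | 94.9% |

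Without a standard deviation, the percentages in step 3 cannot be converted to this scale. The two illustrations stand separately.

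**5. Effect on the contrast between legs.** Let C and K be the true changes in the copper and control legs, and b a drift common to both. The contrast is (C + b) − (K + b) = C − K, so b drops out. A simulation (50,000 runs, n = 15, assumed correlation of 0.5 between the legs' changes, common drift of 0 to 0.75 SD) gave false-positive rates of 4.8% to 5.0% for this contrast. If the drift is proportional, as in step 3, the leftover on the raw scale is the drift fraction times the difference in the two legs' areas. Because the copper side is marked at random, that leftover averages zero.

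**6. Timing of unblinding.** Recruitment lasts three months and each patient is followed for 8 weeks. A patient recruited on the last day has 8 weeks of follow-up left when the guarantee on the envelope ends. Reading images before allocation is revealed is therefore not secured by the present text.

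**The case against.** The strongest reply is that the question the trial asks is about copper, and the blinded control leg already answers it. Step 5 supports this: drift common to both legs does not disturb that contrast. Moreover, both legs wear compression, so change from baseline cannot isolate copper however the images are read. Both points stand, and they limit how much this matters.

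Four stronger readings are tempting, and the protocol supports none of them.
- A reader might infer that images **are** read with the visit visible. The text is silent, and the datasheet in Appendix 4 is not part of the text available. The most that can be said is that no masking is described.
- A reader might infer that borders **are** drawn by an operator. The text does not say so. If the software finds them, expectation has less room to act.
- A reader might extend the point to the copper-versus-control contrast, for example through different operators for different legs or visits. Nothing in the protocol says that operators change.
- A reader might take 10% to 19% as an estimate. It only restates an assumed shortening of 5% to 10%.

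The expectation argument can also be challenged. The Background ties early improvement to copper and says that ordinary stockings do not improve the skin, so a blinded reader might expect improvement in one unknown leg and not in both. This weakens expectation as a source of a common shift. It does not remove it, and it does not touch drift in reading habits over the course of the study.

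**Conclusion.** The point holds for the comparison of weeks 2, 4 and 8 with baseline: that comparison is planned, and no protection against knowledge of visit is described for it. Whether bias would follow depends on an operator placing the borders and on the reader knowing the visit, and neither is stated. Its size is unknown; the figures above are illustrations under assumed inputs.

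The copper-versus-control contrast is not affected by drift that acts equally on both legs, and it remains the comparison that bears on copper. Masking visit would remove one source of error from the baseline comparison but would not turn it into evidence about copper as distinct from compression or the passage of time. This is a worthwhile minor improvement, not a flaw that undermines the trial.

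**What to change.** Two short changes to the text are needed.

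- **Eykona® Wound Measurement System:** state that all images are measured as one batch, after the last week-8 visit and before allocation is revealed, by one existing team member, in computer-generated random order. Patient code, leg and visit date are hidden from that reader, either by automated renaming of the files or by another existing team member.
- **Randomisation:** keep the allocation envelope closed until follow-up and image measurement are complete, and not only while patients are being recruited. Without this, the first change does not secure reading before unblinding.

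The images are stored, so nothing in the protocol requires them to be measured in visit order. No extra patients, visits, procedures or staff are needed. The downside is small: files must be recoded, and skin results are available only after the last visit. A single reading will still give no estimate of repeatability.

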# Statistical analysis

Statistical analysis will be performed using SPSS version 20.0 or higher. The CEAP classification, the Venous Clinical Severity Score and the AVVQ score at the 2, 4, and 8 weeks assessment will be compared with the baseline scores. The length, width and surface area of the skin condition from the leg with the copper will be compared with the control leg and the measurements at the 2, 4, and 8 weeks assessment will be compared with the baseline measurements. Paired t-test will be used for continuous data at baseline and a multilevel (mixed) regression model will be used to analyse the change over time.

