# **CEAP Clinical classification of chronic venous disease**

The prevalence of CVD varies among the different stages of the disease. A large worldwide study of the Vein Consult Program showed a prevalence of clinically significant CVD of more than 60% in the general population (4). Varicose veins are the most common manifestation

of CVI with a prevalence up to 30% in adult population (1,2,3). The prevalence of active and healed ulcers is approximately 1% of the adult population (5). Since delayed healing and recurrence are very common, the prognosis of venous ulceration is poor (6).

The high prevalence and the chronic nature of venous disease have a considerable socioeconomic impact. A study conducted in the United States and the United Kingdom showed that venous ulcers cause a decrease of 2 million working days per year (7) and the National Health Service (NHS) spends approximately 1-3% of the total health care budget on the treatment of CVD (8,9).

Graded compression stockings are the primary conservative treatment in patients with CVI. A significant improvement can only be achieved with a good compliance (10). Reduced adherence to compression therapy is a well-known and major issue in the treatment of patients with CVD (13). Patients with clinical CEAP classification C4 venous disease, or higher, have an increased risk of venous ulceration. Non-compliance with compression hosiery and deterioration of the skin condition increases this risk. In literature the non-compliance ranged from 22%-67% (13 - 17). The most common reasons for non-compliance are inapplicability, the perception of inefficacy and the lack of comfort (13). However, the strategy to properly address non-compliance remains unknown.

Standard compression stockings reduce the symptoms of pain and oedema, facilitate the healing of ulcers, and prevent the recurrence of venous ulcers (11), but they do not improve the skin condition. Copper has been shown to promote angiogenesis and therefore it could support wound healing and possibly improve skin condition. Copper has also been shown to have strong antimicrobial properties. It has been shown in observational, non-randomised trials that improvement of the skin condition could be seen within two weeks (33,34). When no change in skin condition is seen within four weeks, it is unlikely to be seen at all.

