# **Objectives**

# Primary:

To assess the effect of copper stockings on symptoms in patients with lipodermatosclerosis secondary to venous insufficiency.

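### The plan compares CEAP, VCSS and AVVQ with baseline only, so the stated analysis of symptoms cannot separate copper from compression

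*Combined protocol and SAP*

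**What the plan says.** The primary objective reads: "To assess the effect of copper stockings on symptoms in patients with lipodermatosclerosis secondary to venous insufficiency". The section on patient data and examination assigns subjective symptoms to the AVVQ and treats CEAP and VCSS as objective signs graded on each leg. No primary endpoint is named.

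Each patient wears a copper stocking on one leg and a plain one on the other, both giving 14-18 mmHg of compression (Copper impregnated stockings).

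The Statistical analysis section then takes the outcomes in three steps:

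- For the scores, with CEAP opening the sentence: "the Venous Clinical Severity Score and the AVVQ score at the 2, 4, and 8 weeks assessment will be compared with the baseline scores". No leg comparison is mentioned.
- For the skin measurements: "The length, width and surface area of the skin condition from the leg with the copper will be compared with the control leg". Follow-up is also compared with baseline.
- On methods, a paired t-test is named for continuous data at baseline, and "a multilevel (mixed) regression model will be used to analyse the change over time". No leg or treatment term is given.

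The AVVQ section says that most questions are asked for each leg and that the legs can therefore be compared. The only scoring it describes is a single 0-100 scale for the patient.

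**The concern.** The control leg is there to remove whatever affects both legs: compression, time, regression to the mean, and the attention that comes with being in a study. The stated comparison for the scores does not use it. Compression is not a negligible part of this, because the background section itself says: "Standard compression stockings reduce the symptoms of pain and oedema". The AVVQ section lists pain and oedema among the items that the questionnaire covers.

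Followed as written, the plan could show AVVQ improving from baseline with no means of telling whether copper contributed. A reader could take an improvement common to both legs as a copper effect. The explicit leg contrast is attached to the skin measurements, which serve the secondary objective, and is absent for the instrument that serves the primary one.

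**Working it through.** The plan has no figure to reproduce. The Sample size calculation section sets 15 patients by availability over three months and gives no SD, effect size, significance level or power. The calculation below is therefore an illustration.

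**Inputs.** From the documents: n = 15; four visits (baseline and weeks 2, 4 and 8); one copper and one control leg per patient. Assumed: no copper effect; two-sided 5% level; complete data; an improvement d common to both legs, in SDs of the change from baseline, ranging from 0.1 to 0.8.

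**Step 1: week 8 versus baseline.** The test statistic follows a non-central t distribution with non-centrality d × √15 = 3.873d. A random-intercept model with four visits has 14 × 3 = 42 degrees of freedom; a simple paired t-test has 14. The probability of a significant result is:

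| Shared improvement d | Non-centrality | Mixed model, 42 df | Paired t-test, 14 df |
|---|---|---|---|
| 0.1 | 0.39 | 6.7% | 6.5% |
| 0.3 | 1.16 | 20.6% | 19.2% |
| 0.5 | 1.94 | 47.3% | 43.8% |
| 0.8 | 3.10 | 85.7% | 82.1% |

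**Step 2: copper leg minus control leg.** If both legs improve by d, the difference in change is d − d = 0 whatever d is, so the test keeps its 5% level. Simulation of 20,000 trials per setting, with d = 0.3, 0.5 and 0.8 and equal patient, leg and residual SDs, gave 4.9%, 5.1% and 5.0% for the paired leg difference. A mixed model with leg nested in patient gave 5.2%, 5.0% and 5.0%. In the same trials the mixed-model comparison with baseline was significant in 20.4%, 47.9% and 85.2%. A separate simulation of the paired leg difference, with between-leg correlations of 0.3, 0.5 and 0.7, gave 4.8% to 5.1%.

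**Step 3: precision of the leg contrast.** The half-width of the 95% interval, in SDs of the paired leg difference in change, is:

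- paired analysis: t(0.975, 14)/√15 = 2.145/3.873 = 0.554;
- mixed model with leg within patient: t(0.975, 84)/√15 = 1.989/3.873 = 0.513. The 84 degrees of freedom are 30 legs × 3 = 90, less 3 for visit and 3 for leg type by visit.

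**Step 4: why the leg term matters.** With patient as the only random effect, variation between legs goes into the residual. In the simulation the leg contrast then rejected in only 1.5% to 1.6% of trials. The mean half-width was 1.28 residual SDs, against 1.02 with leg within patient and 1.09 for the paired analysis.

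**Step 5: CEAP.** Every leg enters in class 4 (Methodology). In an exact sign test, five patients whose legs differ, all in one direction, give 2 × 0.5⁵ = 0.0625; six give 2 × 0.5⁶ = 0.031. At least six such patients are needed for p < 0.05.

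**The case against.** The strongest reply is that a leg comparison was plainly intended. The AVVQ section gives the ability to compare legs as a merit of the instrument, CEAP and VCSS are graded by leg, and a multilevel model naturally nests legs in patients. A paired test at baseline may well mean leg against leg. That shows intent, but it does not fill the gap. A baseline comparison of legs says nothing about the effect of copper, and no leg or leg-by-visit term is written down. Step 4 shows that the form of the model changes the answer.

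The percentages in Step 1 are also, strictly, the power to detect a real shared improvement. They become errors only if the change is credited to copper, and nothing in the plan says that it will be. This stands. The shared improvement may also be small, since current stocking users are not excluded.

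This is a feasibility pilot with no declared success rule, which lowers the weight of any test. Its data are nevertheless meant to support a power calculation for a larger trial. If that trial compares copper with control, it needs the between-leg difference and its SD, which the stated analysis of the scores does not produce.

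Finally, the appendix datasheets were not available for this review, so a per-leg AVVQ rule may exist there. A formal CEAP test is unlikely to be informative with 15 patients; that is a minor part of the point.

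**Conclusion.** The concern holds. As written, the analysis of CEAP, VCSS and AVVQ does not isolate an effect of copper, and the plan for the AVVQ therefore does not answer the primary objective. This rests on the text alone: a baseline-only comparison for the scores, compression on both legs, and the protocol's own statement about what compression does.

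The size is conditional. The chance of a significant change with no copper effect runs from about 7% to 86% for shared improvements of 0.1 to 0.8 SD, and that range is assumed. The design and most of the data collection already support the right contrast, so this should be corrected in the plan and calls for no redesign. Confidence is medium, because the appendices were not seen and the intent to compare legs is visible elsewhere.

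**What to change.** In the Statistical analysis section:

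1. Define a per-leg AVVQ score from the leg-specific questions, or cite the rule if the appendix has one. Report the 0-100 total descriptively.
2. State the main contrast for AVVQ, VCSS and CEAP as change from baseline in the copper leg minus change in the control leg. Give an estimate and 95% interval for AVVQ and VCSS.
3. For AVVQ and VCSS, fit the planned mixed model with leg type, visit and their interaction, and random effects for patient and for leg within patient. Alternatively, analyse the paired leg difference in change.
4. For CEAP, tabulate class by leg and visit. If a comparison is wanted, use a paired ordinal method such as an exact sign test.
5. Keep the comparison with baseline as descriptive.

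The cost is a scoring rule and a few sentences, with no new data or visits. There are two drawbacks. A per-leg AVVQ is not the published total and leaves out the questions that are not leg-specific. The contrast will also be imprecise: a half-width of about 0.55 SD of the paired difference, or 0.51 SD in the mixed model if its constant-variance structure holds.
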